Subjects: Participants will be 150 treatment-seeking Veterans or family members of Veterans (including National Guard and Reservists) between the ages of 18 and 70 with chronic pain BPI pain on average score \geq 4/10; \geq 3 months duration of pain) and a prescription opiate use disorder (past 6 months; COMM score \geq 7). Specific inclusion and exclusion criteria can be found in the Human Subjects Section. The actigraphy sleep measures will be gathered in ~90 (all participants that enroll going forward) of the planned 150 participants in our sample (~75% of the sample).

[figure not shown]
Recruitment: The primary recruitment site will be the outpatient Ralph H. Johnson's VAMC Pain Management Clinic (PMC). Data from 2012 indicate that 39,436 opioid analgesic prescription orders (exclusive of refills) were provided to 8,189 unique patients at our VAMC. To date, 2013 data indicate that 33,136 prescription orders (exclusive of refills) for opioid analgesics have been provided to 7,447 unique

patients. Consults for pain management are made directly to the PMC's Interdisciplinary Pain Team, which includes an Anesthesiologist ([name]), a Health Psychologist ([name]; PMC Recruitment Liaison for this study), a Pharmacist ([name]; and nursing staff. Data from October 2012 – August 2013 indicate that the PMC completes approximately 68 new-patient pain consultations each month (816 new patients per year)). Approximately 60% of all patients seen in the PMC have a diagnosis of CLBP (41 CLBP patients per month). For the proposed study, we need to enroll 24 Veterans or family members per year. As such, there should be no problem with adequate subject recruitment in order to complete the study within the timeline proposed. See the Facilities and Resources section for more information about the PMC.

While recruitment will be primarily from patients presenting to the VAMC's PMC, potential participants will be allowed to self-refer in response to signage on CARTA transit vehicles; newspaper, television and radio advertisements; research-specific websites (e.g., ResearchMatch.org, SCResearch.org, study site, etc.); and advertisements posted on social media sites (e.g., Craigslist, Facebook, Reddit, etc.). Furthermore, IRB-approved recruitment materials will be posted and/or disseminated across the community, as well as VAMC and MUSC clinics.

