Alternately, the participant can provide BP documentation from a medical professional (within the past 6 weeks) and/or a study team member can view the participant's EPIC/CPRS record for a recent BP value. Self-report measures of pain, opiate misuse, depression, anxiety, PTSD, and sleep functioning will also be assessed at baseline and throughout the study.

During the baseline phase, eligible participants will have their cell phones registered into the *daily diary system* described below and will be given instructions on how to respond to daily queries regarding pain, mood, craving, etc. Patients without a cell phone will be provided a cell phone for use during the study. Actigraphy monitors will be provided for all participants for sophisticated measurement of sleep patterns that will allow investigators to examine (1) the impact of the investigational treatments on sleep patterns, (2) the temporal co-variation in sleep and pain, and (3) potential mediation effects of sleep on pain and opioid misuse. Eligible participants will then complete a 2-week baseline period during which daily diary assessments are obtained. During the 2-week baseline phase, patients will undergo structural and functional MRI scanning and QST procedures (described in more detail in the Study Interventions and Procedures section). These procedures will be repeated at the end of treatment.

Immediately following the baseline period, subjects will receive 11, 60-min sessions of manualized, individual CBT for pain delivered once a week over approximately 11 weeks. Therapy sessions may be delivered via doxy.me with the subject in an MUSC office at a standard desk using a laptop computer. Subjects will be randomized to receive real or sham tDCS during the therapy sessions. Within 3 weeks following completion of the CBT treatment, participants will repeat the neuroimaging and QST procedures. They will return at 1-, 3-, and 6-months post-treatment for follow-up visits. If participants are not able to return in person for the follow up visits, participants can complete the follow up assessments on REDCap, entered directly into the online portal to ensure security and prevent data loss.

Actigraphy measurement of sleep patterns will be recorded after the 2-week baseline period, post treatment, and at 1-, 3-, and 6-months post-treatment follow-up visits.

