Primary Outcome Measures: The primary measures are described in this section. Information regarding additional measures can be found in Table 1. (1) **Pain:** *Electronic Daily Diaries* will be administered using either standard feature or smart cell phones. The MUSC Technology Applications Center for Healthful Lifestyles (TACHL), directed by [name] (Co-I), will adapt software they originally configured for a daily monitoring protocol of PTSD symptoms. The pain/mood/craving/opiate-use questions will assess daily (via numeric rating scale; NRS) average pain, pain at its worst, pain unpleasantness, mood, activity-level, sleep quality, hours of sleep, opiate cravings, and will assess amount of prescription opiate. TACHL developed a SMS (Short Message Service)/MMS (Multimedia Messaging Service) encrypted gateway which enables ecological momentary assessment of pain, craving, etc. This communication system was selected due to its flexibility and ready availability for use on all cell phone types and their carriers. Measures will be collected at random times during waking-hours each day to minimize response bias associated with event-related reporting. See the Facilities and Resources section for more information on TACHL. The *Brief Pain Inventory (BPI)* is a widely used, 17-item self-report measure that assesses pain intensity and interference. Patients rate pain severity as well as the degree to which pain interferes with seven aspects of life: Work, Activity, Mood, Enjoyment, Sleep, Walking, and Relationships. (2) **Opiate Use Severity:** The *Current Opioid Misuse Measure (COMM)*^{68, 69} is a brief, 17-item measure designed to monitor chronic pain patients on opioid therapy. It assesses medication misuse behaviors such as, obtaining additional opiates from other doctors or the emergency room; taking medication that belongs to someone else; taking more opiates than prescribed; using opiates for alternative reasons (e.g., to reduce anxiety); consuming opiate medication via alternative route

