Quantitative Sensory Testing (QST): Secondary objectives of the study are to evaluate acute lab-based pain markers. QST provides indices of changes in specific peripheral and central nociceptive and proprioceptive processing. Using QST we will assess: (1) *mechanical pain threshold* using the IITC Life Sciences Digital Anesthesiometer applied to the distal phalange of the digiti minimi of the left hand (increased at rate of 10grams/sec; pressure recorded in grams). (2) *thermal pain tolerance* using 5 trials of cutaneous heat stimuli via the ATS thermode. (3) *thermal wind-up pain* will be assessed with the CHEPS thermode, which will deliver 20 brief (0.75s) suprathreshold thermal stimuli selectively stimulating C-fibers. During 30sec of repeated heat stimulation, subjects will indicate their level of pain severity using a visual analogue scale. This QST paradigm will provide preliminary data about any selective effects of the interventions on A- δ , A- β , and C-fiber activation as well as yield preliminary mechanistic information about unique effects of CBT+tDCS on sensory versus affective dimensions of the pain experience.

Sleep Monitoring: Participants will be given actigraphy monitors at the time of study enrollment that employ a validated 3-axis accelerometer and data filtering technology, and contains a gyroscope, magnetometer, and secondary accelerometer to deliver valuable information about movement, rotation, and body position. The objective measures yielded by the device include: Raw Acceleration, Energy Expenditure, MET Rates, Steps Taken, Physical Activity Intensity, Activity Bouts, Sedentary Bouts, Heart Rate R-R intervals, Body Position, Sleep Latency, Total Sleep Time, and Sleep Efficiency. An advanced wear time sensor on the back of the device uses capacitive touch technology to automatically detect when a wrist worn device has been removed for simplified compliance monitoring and data cleaning. We will primarily be gathering daily information regarding sleep latency, total sleep time and sleep efficiency. This information will permit detailed examination of the role of sleep, chronic pain and opioid use among veterans and family members.

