Time-Series Variables: The actigraphy devices will yield time-series data including sleep latency, total sleep time and sleep efficiency. Hierarchical Linear Modeling (HLM) will be applied to evaluate daily (time-series) pain, craving, opiate used, mood, anxiety, and physical activity ratings throughout the 3 phases of the study (baseline, treatment, and follow-up) and by group. The covariance structure of the model will be set to first-order autoregressive and independent effects of treatment on average daily pain will be assessed by controlling for daily fluctuations in craving, mood, anxiety, and activity in the model. Additional co-variates of CBT-related effects will include therapeutic alliance and pain coping styles. Additionally, cross-lag correlational analyses will be conducted on pain, craving, mood, anxiety, and activity data to estimate temporal order of changes during the trial.

Repeated Measures Variables: BPI, COMM, as well as mean weekly sleep latency, total sleep time and sleep efficiency scores will be examined with HLM using an unstructured covariance matrix. Subject-level intercepts will be entered into the model at level-1, and a time X group (real vs. sham tDCS) mixed model will be implemented. The primary model parameter of interest will be the time X group interaction term; however, main effects will be specified in the model. Effects of treatment on pain and opioid misuse will be separated from mood effects by co-varying mood and anxiety ratings at the individual subject-level.

Power: Effect sizes (Cohen's d) for CBT for chronic pain range from 0.3 to 1.4. A realistic effect-size estimate for the CBT intervention would be categorized as "medium/modest" (d=.5). The effect-size associated with clinical effects of tDCS on chronic pain in the current literature is also medium/modest (d=.5). With 150 subjects (75 in each group), power to detect effects (alpha=.05, effect-size d=.5, r among repeated measures=.5) is good to excellent (1- β = .80 and .99, respectively). Power will be higher for the HLM model as sources of intra-class variability are better managed.

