fMRI power to detect effects for planned contrasts was estimated as function of N, mean difference in percent signal change between block/conditions (μ_D), within-subject variability over time (σ_W), and between subject variability (σ_B) based on previous work conducted by our group. The effect size for our previously employed pain minus rest contrast was 1.8. Thus, power (1- β) reaches .80 with only 12 participants per group (two-tailed, alpha=.01). The present study is therefore well-powered to identify significant connectivity and activation patterns using the pain-rest block paradigm and functional connectivity methods proposed.

Hypotheses: The hypotheses and statistical approaches for testing each hypothesis is as follows:

Hypothesis 1a: CBT + real tDCS will result in significantly greater improvements, as compared to CBT + sham tDCS, in average daily pain (electronic diary), pain unpleasantness (electronic diary) and functional impairment due to pain (BPI). To test this hypothesis, time-series analysis of diary average pain and pain-unpleasantness ratings will be conducted and BPI total scores will be used as repeated measures variables using the HLM methods and model co-variate strategies delineated above.

Hypothesis 1b: CBT + real tDCS will result in significantly greater improvement, as compared to CBT + sham tDCS, in sleep latency, total sleep time and sleep efficiency. To test this hypothesis, time-series analysis of actigraphy sleep latency, total sleep time and sleep efficiency values will be used as repeated measures variables using the HLM methods and model co-variate strategies delineated above.

Hypothesis 1c: Sleep latency, total sleep time, and sleep efficiency will improve significantly after the manualized CBT module devoted to sleep hygiene compared to other CBT modules. To test this hypothesis, interrupted time-series analysis (via HLM) will be conducted with the "Sleep Hygiene" CBT module established as the temporal demarcation point.

Hypothesis 1d: Time-series data representing sleep latency, total sleep time and sleep efficiency *improvements will lead* any observed *improvements* in pain and functioning consistent with emerging data on the temporal relationship between sleep and pain.⁷⁹ To test this hypothesis, lead-lag analysis of key time-series variables (sleep latency, total sleep time and sleep efficiency, pain and functional impairment due to pain) will be conducted.

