Hypothesis 2a: CBT + real tDCS will result in significantly greater reductions, as compared to CBT + sham tDCS, in COMM scores and opiate craving ratings (electronic diary) compared to CBT + sham tDCS. To test this hypothesis, time-series analysis of diary ratings of opiate cravings will be conducted and COMM total scores will be used as repeated measures variables using the HLM methods and co-variate strategies delineated above.

Hypothesis 2b: CBT + real tDCS will result in significantly greater reductions, as compared to CBT + sham tDCS, in depression (BDI-II), anxiety (BAI), PTSD (PCL-M) and sleep (PSQI). To test this hypothesis, total scores on the identified measurements will be used as repeated measures variables using the HLM methods and co-variate strategies delineated above.

Hypothesis 2c: Total sleep time will mediate the clinical benefits of combined CBT-tDCS on chronic pain. To test this, structural equation modeling (SEM) will be used to examine the amount of variance explained in clinical improvement related to tDCS+CBT with and without total sleep time entered into the temporally dynamic model.

Hypothesis 3a: At baseline, percent BOLD signal change in the left DLPFC during pain blocks will be inversely related to BOLD signal in the left insula, ACC, thalamus, caudate, putamen, and medial prefrontal cortex.

Hypothesis 3b: After treatment, percent BOLD signal change in the left DLPFC during pain blocks will be significantly greater in the CBT + real tDCS group as compared to CBT + sham tDCS.

Hypothesis 3c: Functional connectivity between the left DLPFC and insula and ACC after treatment will be greater in participants who receive CBT + real tDCS as compared to CBT + sham tDCS.

Hypothesis 3d: The change in functional connectivity will be correlated with changes in pain (BPI), opiate use severity (COMM), and total sleep time.

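### The cross-lag correlations planned to establish temporal order confuse a series' persistence with its direction, and the Hypothesis 1d lead-lag analysis states no protection against the same error

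*Combined protocol and SAP*

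**What the plan says.** Two places deal with temporal order.

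- Statistical Analyses and Power, Time-Series Variables: "cross-lag correlational analyses will be conducted on pain, craving, mood, anxiety, and activity data to estimate temporal order of changes during the trial". Sleep is not in this list.
- Hypothesis 1d, on whether improvement in sleep precedes improvement in pain and functioning: "lead-lag analysis of key time-series variables (sleep latency, total sleep time and sleep efficiency, pain and functional impairment due to pain) will be conducted". No statistic, lag, own-lag term, detrending or decision rule is given.

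Two nearby statements could be read as covering the gap. In Time-Series Variables, "The covariance structure of the model will be set to first-order autoregressive", but that sentence concerns the hierarchical model for daily ratings. Hypothesis 2c compares a structural equation model "with and without total sleep time entered into the temporally dynamic model". It addresses mediation and states no autoregressive paths.

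On the data available:

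- Subjects section: "The actigraphy sleep measures will be gathered in ~90" of the 150 participants.
- Sleep Monitoring: "We will primarily be gathering daily information regarding sleep latency, total sleep time and sleep efficiency".
- General Procedures: "Actigraphy measurement of sleep patterns will be recorded after the 2-week baseline period, post treatment, and at 1-, 3-, and 6-months post-treatment follow-up visits".
- Primary Outcome Measures: the diary items are three pain ratings, mood, activity level, and "sleep quality, hours of sleep, opiate cravings, and will assess amount of prescription opiate". Anxiety is not listed, although Time-Series Variables treats it as a daily rating.
- Safety and Monitoring Plan: BPI and BAI are monitored weekly.

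**The concern.** A lagged correlation mixes two things: any effect of one series on the later value of the other, and the carry-over of a same-day association through the later series' own persistence. A series that changes slowly from day to day still resembles yesterday's value, so whatever was correlated with it yesterday is correlated with it today. Comparing the two lagged correlations can therefore show which series is more persistent and nothing about which moves first. Stable differences between people, and improvement shared by all series during CBT, add lagged correlation in both directions.

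At stake is a mechanism claim. The temporal relation of sleep and pain is one of the stated reasons for the actigraphy, and Hypothesis 1d sits under Specific Aim 1. A direction could be reported, for sleep and pain or for pain, craving, mood and activity, with no lagged effect behind it.

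**Working it through.** The documents give no figure for these analyses, so there is none to reproduce. The check asks what the comparison of lagged correlations returns when no lagged effect exists.

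**Inputs.** From the documents: about 90 people with actigraphy; 11 weekly sessions, so 11 × 7 = 77 days if sleep is recorded daily through treatment; a 2-week baseline diary, so 14 days; alpha 0.05 (taken as two-sided). Assumed, because the documents are silent: the own-lag coefficients phi_sleep and phi_pain, and the same-day correlation r.

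**Closed form.** For two stationary first-order autoregressive series with no cross-lagged effect:

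- corr(sleep on day t-1, pain on day t) = phi_pain × r
- corr(pain on day t-1, sleep on day t) = phi_sleep × r

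With phi_sleep = .2, phi_pain = .6 and r = -.3, these are .6 × (-.3) = -.18 and .2 × (-.3) = -.06. Sleep appears to lead.

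**Simulation.** No lagged effect, 90 people, per-person lag-1 correlations, Fisher z, paired t-test of the two directions. Results are rounded; simulation error is one to two percentage points.

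| phi sleep / pain | r | Expected lag correlation, sleep first / pain first | False leader, 77 days | False leader, 14 days |
|---|---|---|---|---|
| .2 / .6 | -.30 | -.18 / -.06 | sleep, 100% | sleep, about 92% |
| .2 / .5 | -.15 | -.075 / -.03 | sleep, about 84% | sleep, about 20% |
| .2 / .6 | -.10 | -.06 / -.02 | sleep, 79% | sleep, 20% |
| .3 / .5 | -.20 | -.10 / -.06 | sleep, 74% | sleep, 18% |
| .1 / .3 | -.15 | -.045 / -.015 | sleep, 47% | sleep, 11% |
| .4 / .4 | -.20 | -.08 / -.08 | about 3% each way | about 3% each way |
| .2 / .6 | 0 | 0 / 0 | about 3% each way | about 3% each way |
| .6 / .2 | -.30 | -.06 / -.18 | pain, 100% | pain, 91% |

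In the equal-persistence row no direction is favoured, yet the sleep-to-pain lag correlation taken alone is significant in 100% of trials at 77 days and 29% at 14 days.

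**Change scores.** For first differences the lagged covariances are -r(1 - phi_pain)² with sleep first and -r(1 - phi_sleep)² with pain first. In the top row these are .3 × .16 = .048 and .3 × .64 = .192. Dividing by √(1.6 × .8) = 1.131 gives correlations of about .04 and .17, so the asymmetry reverses.

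**Adding the outcome's own lag.** Regressing pain on yesterday's pain and yesterday's sleep, in the top-row setting, makes the sleep coefficient zero in expectation: (-.18 + .3 × .6)/(1 - .09) = 0. The simulated false-positive rate falls to about 6 to 8% at 77 days and 8.5% at 14 days.

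**Limit of that adjustment.** Add measurement error of 0.3 of the true variance to both series (an assumption). The observed variances become 1.3 and the sleep coefficient is [1.3 × (-.18) + .3 × .6]/(1.3² - .3²) = -.054/1.6 = -.034. That is small, but it is declared different from zero in about 88% of trials at 77 days and 31% at 14 days.

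**The case against.** The strongest reply is that Hypothesis 1d does not commit to correlations. Lead-lag analysis can mean a lagged regression with own-lag terms, and the sentence that does name correlations leaves sleep out. This stands. A reader might infer that the plan will confirm Hypothesis 1d by construction, but the documents do not support that. For sleep and pain the fault is that nothing excludes the faulty comparison. For pain, craving, mood, anxiety and activity the faulty method is named.

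A reader might also infer that sleep must always appear to lead. It need not. The artefact requires a non-zero same-day correlation and analysis in levels, and its direction depends on which series is more persistent. No document says that this is pain. The plan also speaks of the order of changes and of improvements, so an analysis of change scores is possible, and there the asymmetry reverses.

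The 77-day figures presuppose nightly actigraphy throughout treatment. Sleep Monitoring supports that, as do the weekly sleep means under Repeated Measures Variables and the Hypothesis 1c analysis around the sleep-hygiene session. General Procedures lists only set time points. With 14 days the weaker settings fall to 11 to 20%.

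Finally, it is tempting to say that anxiety and BPI impairment cannot be lagged at all. That goes too far. Time-Series Variables refers to daily anxiety ratings, the description of the diary in General Procedures is open-ended, the contents of Table 1 are not legible in the available text, and BPI and BAI are monitored weekly. A weekly lagged analysis is feasible. What remains is an inconsistency about frequency.

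**Conclusion.** The concern holds in a limited form. The cross-lag correlations under Time-Series Variables cannot establish temporal order, because differential persistence alone can produce a leader in either direction. The Hypothesis 1d analysis is open to the same error because no own-lag adjustment is stated. The false-lead rate runs from chance to 100% over the assumed settings. It depends on the autocorrelations, the same-day correlation and the number of paired days, none of which the documents settle. More days make it worse.

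The randomised comparison of real with sham tDCS is untouched, as are safety and data collection. The point is therefore one that should be fixed, and it bears only on the mechanism claims.

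**What to change.** Before analysis:

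1. Replace the cross-lag correlations, and specify the Hypothesis 1d lead-lag analysis, as a multilevel lag-1 model. Regress each outcome on its own previous value and on the previous value of the other series, with person-mean centring, person-level random effects and a time or phase trend. Fit and report both directions.
2. Judge direction on the size and 95% confidence interval of the two lag coefficients, not on significance alone. Add a measurement-error allowance or sensitivity analysis, for example a latent dynamic model.
3. Lag only series measured at the same frequency, such as diary items with nightly sleep, or weekly BPI with weekly mean sleep.
4. Reconcile Sleep Monitoring (daily sleep data) with General Procedures (actigraphy at set time points), and the daily anxiety ratings in Time-Series Variables with the diary items in Primary Outcome Measures.

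The cost is SAP wording and some modelling time. No new data are needed if sleep is already recorded nightly during treatment; if it is not, the lead-lag question must be confined to the periods that have paired data. The likely downside is a smaller and less certain lead effect.

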Neuroimaging Procedures: Functional MRI (fMRI) data will be acquired from all participants 1 week before and within 3 weeks of completion of the 11-session CBT protocol. The scans will be conducted at the MUSC Center for Biomedical Imaging, which is also designated as VA-approved space. High-resolution structural scans will be obtained at the beginning of each session using an inversion recovery 3D spoiled gradient echo (3DSPGR) sequence, 128 slices, matrix size: 256 x 256, field of view: 24 cm, section thickness: 1.5 mm with no gap between sections, giving an in-plane resolution of 0.94 mm. This sequence will be used for anatomic overlays of the functional data, for spatial normalization to a standard atlas, and subsequent voxel-based morphometry (beyond the scope of this proposal). Outside the scanner, participants will undergo a thermal method-of-limits procedure (aided by parameter estimation by sequential testing) to determine the temperature output required from the Medoc Pathway System to reliably produce a subjective NRS pain rating of 7/10. This temperature will be delivered in 12-second tonic blocks interspersed with 18-second rest/pain rating periods during the fMRI sequence. The data will be preprocessed in accordance with standard practice in our laboratory using SPM 8 (Wellcome Department of Cognitive Neurology, London, UK) and the average time courses from anatomically defined regions of interest (ROIs) extracted and analyzed using customized scripts (Matlab 6.5, Mathworks, Natick, MD).

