For hypotheses 3a-3d, we will measure the following dependent variables: (1) percent change in BOLD signal in the left DLPFC as well as other limbic and executive regions of interest (ROIs) including the left and right insula, ACC, thalamus, caudate, putamen, and medial prefrontal cortex; and (2) functional connectivity (quantified as the average correlation coefficient between the ROIs) between the left DLPFC and the aforementioned ROIs will be used to test the hypothesis that CBT and tDCS have a synergistic effect on the neural adaptations in pain-control circuitry (i.e., insula and ACC). We will also investigate the functional connectivity with a negative control region (i.e., the primary visual cortex), which should not be differentially

modulated by either tDCS or CBT treatment. Group analyses will be performed using a random effects model (corrected, $p<0.01$ cluster level, $k= 25$, SPM 8).

Hypothesis 3e: Functional connectivity between the left DLPFC and insula and ACC after treatment will be greater in participants who receive CBT + real tDCS as compared to CBT + sham tDCS, and the change in functional connectivity will be correlated with changes in total sleep time.

HUMAN SUBJECTS RESEARCH

Protection of Human Subjects

Risks to Subjects

[name] is a licensed clinical psychologist with extensive training and experience in conducting human research. The Co-Is also have extensive experience in human research, and Drs. [name], [name], [name], [name], [name], [name], [name], and [name] have all completed the University of Miami computer-based CITI Human Subjects Research Education Course. All research activity, informed consents, and continuing reviews will be reviewed by MUSC's IRB in compliance with 45CFR46 before the research is started and continuing review will occur annually. The research staff will ensure that all information needed for the continuing review is at the IRB in accordance with IRB requirements.

Human Subjects Involvement and Characteristics

A total of 150 adults between the ages of 18 and 70 will be recruited over a 5-year period. The inclusion/exclusion criteria for the study are as follows:

Inclusion Criteria:

1. Ages 18 to 70.
2. United States Veteran or family member of a Veteran.
3. Able to provide informed consent and function at an intellectual level sufficient to allow accurate completion of the assessment instruments.
4. Subjects must be able to comprehend English.

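### The fMRI power statement uses a within-participant pain-minus-rest effect, which gives no support to the real-versus-sham imaging hypotheses (3b, 3c and the first part of 3e)

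*Combined protocol and SAP*

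**What the plan says.** In Statistical Analyses and Power, the fMRI power paragraph lists its inputs as the sample size, the "mean difference in percent signal change between block/conditions", a within-subject variance term and a between-subject variance term, both variances coming from the group's previous work. The only effect size printed is this one: "The effect size for our previously employed pain minus rest contrast was 1.8". Power then "reaches .80 with only 12 participants per group (two-tailed, alpha=.01", and the paragraph concludes: "The present study is therefore well-powered to identify significant connectivity and activation patterns".

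The between-arm imaging hypotheses appear later in the same section:

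- Hypothesis 3b: left DLPFC signal change after treatment "during pain blocks will be significantly greater in the CBT + real tDCS group as compared to CBT + sham tDCS".
- Hypotheses 3c and 3e, which share this opening: "Functional connectivity between the left DLPFC and insula and ACC after treatment will be greater in participants who receive CBT + real tDCS", again compared with sham.

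Under Neuroimaging Procedures, "Functional MRI (fMRI) data will be acquired from all participants 1 week before and within 3 weeks of completion" of the CBT course. The Power paragraph plans 75 participants in each group. It also contains the plan's only tDCS effect size, d=.5, which concerns pain and not imaging: "The effect-size associated with clinical effects of tDCS on chronic pain in the current literature is also medium/modest".

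**The concern.** A pain-minus-rest effect measures how strongly the brain responds to painful heat compared with no heat. Both arms receive the same stimulus, and both should show that response. Its size does not indicate how far the real and sham arms will differ after treatment. For 3c and 3e the mismatch goes further: the outcome is a correlation between regions, which is not on the scale of a block difference in signal at all.

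Aim 3 is one of three specific aims, and every participant is to be scanned twice. If 3b or 3c turns out null, a reader who relied on the plan's power claim could take that as evidence against a neural effect of tDCS. Whether that reading is fair depends on what difference the scans could have detected, and the plan does not say.

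**Working it through.** **Inputs.** From the plan: effect 1.8, 12 per group, two-tailed alpha .01, stated power .80 (fMRI power paragraph); 75 per arm and d=.5 for clinical pain (Power paragraph); all participants scanned before and after treatment (Neuroimaging Procedures). Assumed here, because the plan gives no values: scan loss of 10% to 30%, pre-post correlation r of .3 to .7, and true real-versus-sham d of .3 to .8.

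**1. What kind of effect 1.8 is.** Neuroimaging Procedures has 12-second heat blocks alternating with 18-second rest and rating periods in one fMRI sequence. Pain and rest are therefore measured in the same person in the same scan, so 1.8 is a within-participant contrast.

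**2. The plan's own figure.** Noncentral t, taking 1.8 as a standardised effect (the scale is not stated):

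- Two-group test, n=12 per group: noncentrality 1.8 × √(12/2) = 4.41, df 22, power **.93**.
- One-sample (paired) test, n=12: noncentrality 1.8 × √12 = 6.24, df 11, power above **.99**.

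Neither gives .80. With n=12, power of .80 corresponds to d=1.51 (two-group) or d=1.17 (one-sample). The printed figure is lower than the inputs imply, so the discrepancy is conservative, and the unprinted variance terms may explain it.

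**3. What 75 per arm can detect between arms.** By normal approximation, d = (z.995 + z.80) × √(2/n) = (2.576 + 0.842) × √(2/75) = 0.558. By noncentral t with df 148, d = **.564**.

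Detectable d at 80% power, and power if d=.5, for one unadjusted post-treatment comparison at two-sided alpha .01:

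| Usable scans per arm | Detectable d | Power at d=.5 |
|---|---|---|
| 75 (no loss) | .56 | .67 |
| 67 (about 10% lost) | .60 | .61 |
| 60 (20% lost) | .63 | .55 |
| 52 (about 30% lost) | .68 | .47 |

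At 75 per arm, power is .22 for d=.3 and .99 for d=.8.

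**4. With baseline adjustment.** The effective standardised effect is d/√(1−r²), with df 2n−3. At r=.5:

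- 75 per arm: detectable d .49, power at d=.5 of .82.
- 60 per arm: detectable d .55, power at d=.5 of .71.

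At 75 per arm, r=.3 gives power .73 (rounded up from .725) and r=.7 gives .95 for d=.5.

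**5. Dependence on alpha.** At two-sided .05 instead of .01, the unadjusted detectable d at 75 per arm is .46. Power at d=.5 is then .86 at 75 per arm and .78 at 60.

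The d=.5 rows only illustrate the case in which the clinical-pain effect carries over to imaging. Nothing in the plan says that it does.

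**The case against.** The best defence is that the trial may have reasonable power for these comparisons anyway. Scans are taken before and after treatment, so a baseline-adjusted analysis is available, and at r=.5 it has power .82 for d=.5 with 75 per arm. The alpha is also open to argument: .01 appears in the fMRI power calculation and as the corrected cluster threshold, while the Data Management and Analysis paragraph tests all primary hypotheses at .05. Imaging is not among the primary outcomes listed there, and the sample size is not built on it. Finally, a t test on one value is not the random-effects, cluster-corrected group analysis that the plan describes.

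Much of this stands, and it limits the point. The numbers do not show that Aim 3 is underpowered. The .56 is a benchmark for one region or connection before any multiplicity correction, and it depends on the alpha used. The mismatch at 12 per group is minor.

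It does not rescue the claim. No imaging model with baseline adjustment is specified, 3b and 3c are worded as post-treatment comparisons, and no real-versus-sham imaging effect is given. If the reference to 12 per group was meant as real versus sham, it assumes that the tDCS difference is as large as the whole pain response. If it was meant as pain versus rest, it does not address these hypotheses. The confidence intervals promised for the results will show the precision achieved, but they cannot support a power claim made in advance.

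**Conclusion.** The concern holds. The power claim is supported, at most, for the pain-rest activation contrast. For 3b, 3c and the between-arm part of 3e it has no stated basis. At the plan's n and the fMRI paragraph's alpha, the detectable difference for one unadjusted comparison is d of about .56, assuming that all 150 participants have usable post-treatment scans. It rises to between .60 and .68 with assumed losses of 10% to 30%, and falls to about .49 at 75 per arm with baseline adjustment at an assumed r=.5. Correction across regions or clusters would raise it. These figures do not cover 3a, 3d or the correlation of connectivity change with sleep time in 3e. The arithmetic mismatch in the .80 figure is secondary and does not affect this conclusion. The plan should be corrected, but no design change follows.

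**What to change.** Confine the 1.8, 12-per-group and adequacy statements to the within-participant pain-rest contrast. State which test and variance inputs give .80, or replace that figure.

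For 3b, 3c and the between-arm part of 3e, substitute a detectable effect, for example: *With 75 per arm and two-sided alpha .01, an unadjusted post-treatment comparison of real with sham tDCS for one region or connection, before multiplicity correction, has 80% power for d of about .56, and only for a larger d if scans are lost.* If a baseline-adjusted model is intended, say so and give the assumed pre-post correlation. If the region-level tests are to use .05, say that and give the matching figure (.46 unadjusted at 75 per arm). Alternatively, give a sourced real-versus-sham imaging effect size and the power it implies.

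It would also help to say that the correlational hypotheses (3a, 3d and the second part of 3e) carry no power statement.

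The cost is wording only: sample size, scanning and analysis do not change. The stated imaging power becomes less favourable.
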